2 INTRODUCTION

2.1 BACKGROUND

Trauma is the leading cause of death for Americans ages 1-44 and a major cause of morbidity and mortality worldwide.¹ Tube thoracostomy for drainage of blood and/or air in the thoracic cavity is a common procedure for patients sustaining both blunt and penetrating thoracic trauma. Within the last ten years, smaller bore chest tubes (≤ 20 Fr) are being used with increasing frequency to treat these patients.² Increasing evidence continues to show less pain and similar efficacy of the small-bore tubes^{3,4}. Presently, size 14 Fr catheters are routinely used for pneumothorax and occasionally used for hemothorax. Kulvatunyou et al demonstrated no difference in efficacy between small and large bore (>20 Fr) chest tube size for the treatment of hemothorax. However, the study sample was small and usage of the small-bore catheters was selective. Data regarding complications of tube placement and removal, duration of thoracostomy placement, and complications from different tube sizes particularly in the setting of hemothorax is still lacking^{3,4}.

Catheter related bloodstream infections have been successfully reduced using a bundle including maximal barrier precautions⁶. Literature regarding empyema rates and the use of maximum barrier precautions during thoracostomy tube insertion remains scarce. A well designed prospective study has yet to be developed to properly address the chest tube size in the setting of traumatic hemothorax/hemopneumothorax or empyema rates with the use of maximum barrier precautions

2.2 STUDY RATIONALE

Currently, there are no specific guidelines regarding the optimal chest tube size for the treatment of traumatic hemothorax or hemopneumothorax. The efficacy and safety of large bore tubes for pleural drainage is well documented and is considered standard practice⁷. While a randomized study comparing small vs. large bore chest tubes for pneumothorax has been performed the sample size was small and hemothorax was excluded⁸. The investigators have designed a large randomized clinical trial to address the limitations of the data regarding thoracostomy tube size in the treatment of traumatic hemothorax and hemopneumothorax. The investigators hypothesize that there is safety and efficacy non-inferiority between the different chest tube sizes (Aim 1).

In our previous retrospective study, we saw a decrease in empyema rates with 14 Fr catheters (small bore) for pneumothorax where the use of a large drape is standard of care for barrier protection. This prospective study, also seeks to determine the efficacy of the addition of maximal barrier precautions in the prevention of empyema for patients with hemothorax and/or pneumothorax (Aim 2).

2.3 RISK/BENEFIT ASSESSMENT

2.3.1 KNOWN POTENTIAL RISKS

Some risks from the insertion procedure are:

- Bleeding or infection where the tube is inserted
- Improper placement of the tube (into the tissues, abdomen, or too far in the chest)
- Injury to the lung
- Injury to organs near the tube, such as the spleen, liver, stomach, heart, or diaphragm
- Infection

2.3.2 KNOWN POTENTIAL BENEFITS

- Drainage of blood, fluid, or air from around lungs, heart, or esophagus.

2.3.3 ASSESSMENT OF POTENTIAL RISKS AND BENEFITS

Those patients randomized to 14 Fr. Chest tube insertion may experience less pain, but also may be subject to a higher retained hemothorax rate. No additional risks are being subjected to the patient as tube thoracostomy is standard of care and both devices are FDA approved for drainage of fluid.

3 OBJECTIVES AND ENDPOINTS

OBJECTIVES	ENDPOINTS
	Primary
Aim I: Determine the safety and efficacy non-inferiority between small bore (14 Fr) and large bore (28 Fr) in the drainage of traumatic hemothorax and hemopneumothorax	Endpoint I: Retained hemothorax requiring an additional intervention, either video-assisted thoracoscopic surgery (VATS) or additional thoracostomy tube placement.
	Secondary
	Endpoint II: Duration of chest tube placement
	Endpoint III: Initial drainage from chest tube at 5 minutes
	Endpoint IV: Length of hospitalization
	Endpoint V: Subjective pain score (pre- and post-insertion recorded within 5 minutes of insertion). Assessed with 0 -10 numerical pain scale
	Endpoint VI: Hemodynamic stability post-insertion (determined by vital signs: temperature, heart rate, blood pressure, oxygen saturation)
	Endpoint VII: Time to radiographic resolution of pneumothorax, hemothorax, hemopneumothorax
	Endpoint VIII: Tube specific complications: Air leak, tube malposition, & tube migration
	Endpoint IX: Recurrent pneumothorax/hemothorax/hemopneumothorax after tube removal
	Endpoint X: Readmission to hospital for a chest tube related complication

OBJECTIVES	ENDPOINTS
Aim II: Determine the incidence of empyema in the setting of traumatic pneumothorax, hemothorax, and hemopneumothorax with the addition of maximum barrier precautions	Endpoint Ia: Empyema rate

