1 PROTOCOL SUMMARY

1.1 SYNOPSIS

Title:	Prospective Randomized Evaluation of 14F Thal Tube vs 28 French Chest Tube for Hemothorax and Use of Maximum Barrier Precautions
Phase:	Recruiting
Description of Sites/Facilities Enrolling Participants:	Carolinas Medical Center [name]
Study Description:	Traumatic hemothorax and hemopneumothorax are common diagnoses which are typically treated by placement of a chest tube. A retrospective review has previously shown equivalence between 14 Fr chest tubes and 32 – 40 Fr chest tubes for the non-emergent drainage of hemothorax; however, this study was not randomized. We seek to perform a prospective randomized trial that is adequately powered comparing efficacy of 14 Fr thal tubes to 28 Fr chest tubes for non-emergent drainage of hemothorax and hemopneumothorax. Additionally, we will employ maximal barrier precautions for all chest tube insertions and compare empyema rates to our historical controls for patients with hemothorax, hemopneumothorax, and pneumothorax.
Study Population:	Patients aged 18 and older diagnosed with a traumatic pneumothorax, hemothorax or hemopneumothorax that require non-emergent placement of a thoracostomy tube as part of their care.
Aims:	Aim 1: Determine the safety and efficacy non-inferiority between small bore (14 Fr) and large bore (28 Fr) in the drainage of traumatic hemothorax and hemopneumothorax Aim 2: Determine the incidence of empyema in the setting of traumatic pneumothorax, hemothorax and hemopneumothorax with the addition of maximum barrier precautions [Time Frame: 90 days]
Study Hypothesis	Aim 1: The investigators hypothesize that there is non-inferiority in safety and efficacy between the different chest tube sizes Aim 2: Maximum barrier precautions associated with a decrease in empyema rate.

[figure not shown]

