4 STUDY DESIGN

4.1 OVERALL DESIGN

The proposed study is a single center, prospective, non-inferiority trial evaluating the efficacy of small bore (14 Fr) vs large bore thoracostomy tubes in the setting of trauma at an American College of Surgeons designated Level I trauma center. Each patient will receive a study approved thoracostomy tube as indicated and our standard of care thoracostomy tube Practice Guideline will be followed. The study period is from the time of enrollment (visit day 0) up to 90 days (± 14 days) following the date of thoracostomy tube placement. A total of 645 subjects will be prospectively enrolled.

Aim I will be achieved through a prospective randomized study design which will evaluate thoracostomy tubes placed in the setting of traumatic hemothorax or hemopneumothorax. The efficacy of the thoracostomy tube sizes will be determined by assessing the participants for retained hemothorax which will be defined in this study as any residual blood that cannot be drained after 72 hours of thoracostomy as confirmed by imaging. A total of 252 subjects will be enrolled and randomized in this study group.

Aim II will be achieved through a prospective non-randomized controlled study design in which maximum barrier precautions will be used during chest tube placement for all prospective subjects diagnosed with a traumatic pneumothorax, hemothorax or hemopneumothorax. The prospective subjects will be compared to subjects in a retrospective analysis in which the use of maximum barrier precautions was not standard. Maximal barrier precautions will consist of a thyroid drape, hand hygiene, sterile gown, mask, and gloves. The use of sterile technique will be consistent throughout the prospective study. This will limit the variability between the two treatment arms and allow a more accurate comparison of empyema rates between tube size and sterile technique. The use of prophylactic antimicrobial agents will also be collected for these subjects. A total of 645 subjects will be enrolled in this study group (inclusive of those patients enrolled as part of Aim I).

All participants will be monitored for their need for operative intervention (e.g. VATS), development of empyema, hospital readmission, tube related complications (e.g. tube misplacement, tube migration), and death which occurs between thoracostomy tube placement and follow-up.

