8 STUDY ASSESSMENTS AND PROCEDURES

8.1 EFFICACY ASSESSMENTS

The rates of failure of drainage (primary outcome) will be estimated as proportions and compared between the two groups using a Chi-square test corrected for the non-inferiority hypothesis. The margin of non-inferiority is defined as of 8%.

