9.2 SAMPLE SIZE DETERMINATION

Aim I

This study is a non-inferiority randomized controlled trial comparing placement of 14 French vs. 28 French chest tubes for hemothorax and hemopneumothorax. We hypothesize the rate of drainage failure to be approximately 7% in the large 28 tube size group. With a sample size of n=126 per group, we will have 80% power to detect a non-inferiority margin difference between the group rates of 8% (allowing up to a 15% rate of drainage failure in the small 14 tube size group; $\alpha=0.05$). In our prior study, we saw a 20% vs 6.7% difference in needing additional procedures for pneumothorax with small vs large catheters but these numbers are based on draining air not blood. Sample size analyses were conducted in PASS 13⁹.

Aim II

Calculations of sample size were based on two-group comparisons of empyema rates. With assumptions of empyema rate is 5% in the retrospective group and 2% in the prospective group, 586 patients in each group are needed to achieve a power of 0.8 with $\alpha=0.05$. To account for potential attrition, we will inflate the number of patients by 10% resulting in a total of 645 patients in the retrospective group and 645 patients in the prospective group. The sample size was calculated by using the PASS 15¹⁰.

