9.4.3 ANALYSIS OF THE SECONDARY ENDPOINT(S)

Length of stay will be compared using Poisson regression with a main effect of group. Post insertion pain and vital signs will be compared using analysis of covariance controlling for pre-procedural pain and vital signs, respectively, with categorical group effect. We will compare rates of re-intervention and readmission using chi-square tests for independence (or Fisher's exact tests) and present our findings using relative risks and 95% confidence intervals.

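### Aim 1 claims non-inferiority in safety as well as efficacy, but the margin, the non-inferiority test and the sample size cover drainage failure only

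*Combined protocol and SAP*

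**What the plan says.** Three places make safety part of the non-inferiority claim:

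- Section 3, Aim I objective (worded the same way in the synopsis aims): "Determine the safety and efficacy non-inferiority between small bore (14 Fr) and large bore (28 Fr".
- Synopsis (1.1), study hypothesis: "The investigators hypothesize that there is non-inferiority in safety and efficacy between the different chest tube sizes".
- Section 2.2: "The investigators hypothesize that there is safety and efficacy non-inferiority between the different chest tube sizes (Aim 1".

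The statistical machinery is narrower:

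- Section 4.1 calls the study a "non-inferiority trial evaluating the efficacy of small bore (14 Fr) vs large bore thoracostomy tubes". Safety is not mentioned there.
- Section 8.1, which deals with efficacy and drainage failure, states: "The margin of non-inferiority is defined as of 8" per cent.
- Section 9.2 sizes Aim I on drainage failure: "We hypothesize the rate of drainage failure to be approximately 7% in the large 28 tube size group", and "With a sample size of n=126 per group, we will have 80% power to detect a non-inferiority margin difference between the group rates of 8" per cent.
- Section 9.4.2 applies a chi-square test corrected for non-inferiority to drainage failure and to nothing else.
- Section 9.4.3 says: "We will compare rates of re-intervention and readmission using chi-square tests for independence". It allows Fisher's exact test instead and adds relative risks with 95% confidence intervals.
- Section 8.2 lists the safety endpoints: unanticipated serious events related to tube size, post-insertion instability, additional interventions, procedure-related death, empyema, recurrence and 90-day readmission. The study team and a medical monitor review them, and the recommendation to stop rests on clinical judgement. No margin or test is attached.

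The table of contents lists a Safety Analyses section. In the body, 9.4.3 is followed directly by the interim analyses as 9.4.4, and there is no safety analysis section.

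**The concern.** A non-inferiority claim needs an endpoint, a margin and a test whose null hypothesis is that the new treatment is worse by at least that margin. Aim 1 supplies these for drainage failure. Apart from the overlap of one safety event with the primary endpoint, it supplies none of them for safety, although safety is named in both the aim and the hypothesis.

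The chi-square and Fisher tests in 9.4.3 have equality as their null hypothesis. Failing to reject equality is weak evidence when events are rare and each arm has 126 patients. The aim therefore has a safety half with no decision rule, and the trial could end with a statement about the safety of the 14 Fr tube that its design did not set out to establish. The primary efficacy conclusion is not affected.

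**Working it through.** **Inputs from the documents.** 126 per arm, 80% power, alpha 0.05, 7% drainage failure with the 28 Fr tube, margin 8 points (8.1, 9.2). Empyema planning rates of 5% and 2% (9.2, Aim II).

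**Assumptions.** The documents give no rate for safety events in the randomized comparison and no safety margin. I use 2% and 5% because empyema is on the 8.2 safety list, and I take true rates to be equal in the two arms.

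**1. The plan's own figure.** With equal true rates p and margin M, n per arm = (z_alpha + z_0.80)² × 2p(1−p) / M².
- One-sided 0.05: (1.645 + 0.842)² × 2 × 0.07 × 0.93 / 0.08² = 125.8, so 126. This matches. Power at 126 is 80.1%.
- One-sided 0.025 would need 160, so the stated number corresponds to one-sided 0.05.

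The 126 per arm is therefore fully accounted for by drainage failure at 8 points.

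**2. Smallest margin with 80% power at 126 per arm, one-sided 0.05.** M = (1.645 + 0.842) × sqrt(2p(1−p)/126).

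| Assumed event rate | sqrt(2p(1−p)/126) | Smallest margin | Rate the margin would allow |
|---|---|---|---|
| 2% | 0.0176 | 4.4 points | 2 + 4.4 = 6.4% |
| 5% | 0.0275 | 6.8 points | 5 + 6.8 = 11.8% |
| 7% | 0.0321 | 8.0 points | 7 + 8.0 = 15.0% |
| 10% | 0.0378 | 9.4 points | 10 + 9.4 = 19.4% |

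At 2% and 5% the margin exceeds the event rate, so it would accept more than a doubling.

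**3. Power for given margins at 126 per arm, one-sided 0.05.** Power = Φ(M / sqrt(2p(1−p)/126) − 1.645).

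| Assumed event rate | 3 points | 5 points | 8 points |
|---|---|---|---|
| 2% | 52.2% | 88.3% | 99.8% |
| 5% | 29.0% | 57.0% | 89.8% |
| 7% | 23.8% | 46.4% | 80.1% |
| 10% | 19.7% | 37.4% | 68.1% |

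The normal approximation is a little optimistic. With Newcombe limits and exact binomial probabilities, power at 8 points is 98.3% (2% rate), 86.0% (5%) and 77.5% (7%). At 5 points it is 76.5% (2%) and 52.3% (5%).

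**4. What the difference test in 9.4.3 could detect.** Exact enumeration of the two-sided 0.05 chi-square test at 126 per arm gives 13.3% power for 2% v 4% and 32.2% for 5% v 10%. Expected events per arm are 126 × 0.02 = 2.5 and 126 × 0.05 = 6.3.

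**5. What an interval would show.** With equal observed rates, the one-sided 95% upper limit on the difference is 1.645 × sqrt(2p(1−p)/126): +2.9 points at 2% and +4.5 points at 5%.

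Steps 2 and 3 concern the ability to show non-inferiority. Step 4 shows only how little a non-significant difference test would say.

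**The case against.** Several points on the other side are sound.

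- **Overlap with the primary endpoint.** The primary endpoint is retained hemothorax requiring VATS or an additional tube, and 8.2 lists need for additional interventions as a safety event. Section 2.3.3 names a higher retained hemothorax rate as the possible disadvantage of the 14 Fr tube. That event is largely covered by the powered test and by the interim looks in 9.4.4. The overlap is not complete, since the safety item also includes thoracotomy and tube replacement. The other events on the 8.2 list are outside it.
- **Intervals are already planned.** Section 9.4.3 gives relative risks with 95% confidence intervals for re-intervention and readmission. These are useful, but no bound is set against which to read them, and empyema, recurrence and procedure-related death are not mentioned there for the comparison by tube size.
- **Safety has a review route.** Section 8.2 provides a medical monitor and a report after 20 randomized patients, and 10.1.4 adds a quality assessment nurse. This protects participants but does not test non-inferiority.

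Two stronger readings are tempting, and neither is supported. A reader might infer that 126 per arm can never support a safety non-inferiority claim. Step 3 shows otherwise: with 8 points and a rate of 7% or less, power is about 80% or more. A reader might also infer that the investigators intend to treat a non-significant chi-square result as proof of safety. No section says so; 9.4.3 sets no decision rule.

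**Conclusion.** The concern holds as a mismatch of scope. Non-inferiority in safety is an aim and a hypothesis, but apart from the re-intervention event that largely overlaps the primary endpoint, no safety event has a margin, a non-inferiority test or a sample size. A non-significant result under 9.4.3 would not fill that gap.

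The size depends on assumed rates. If the event rate is 2% to 5%, non-inferiority could be shown with 80% power only at margins of 4.4 to 6.8 points, and the difference test would detect a doubling with 13% to 32% power. An 8-point margin is feasible up to a rate of about 7%, but the plan does not assign it to any safety event. At 2% it would allow a rise to 10%, so it would need its own justification. These figures assume equal true rates and one-sided 0.05 for non-inferiority.

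This should be corrected. It changes neither the primary test nor the sample size.

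**What to change.** Preferred change:

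1. In the synopsis (aim and hypothesis), Section 2.2 and Section 3, limit the non-inferiority claim to drainage failure. This agrees with 4.1.
2. In Section 9.4, add a short safety paragraph: each event on the 8.2 list is reported by arm as a risk difference with a 95% confidence interval, alongside the relative risks already planned.
3. State that a non-significant difference test will not be read as non-inferiority or equivalence.

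Alternative, if the safety claim is to stay: name a safety endpoint, justify a margin for it on clinical grounds, specify the non-inferiority test, and show its power at 126 per arm or the number needed.

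The preferred change costs some wording and a few confidence intervals. Its downside is a narrower claim. The Aim 1 sample size stays at 126 per arm and the primary test is unchanged. The alternative could require more patients if the justified margin is tight: at a 5% rate and a 5-point margin, for example, 235 per arm at one-sided 0.05.

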6.2 INDEX HOSPITALIZATION REVIEW

At the time of enrollment, baseline demographic and injury characteristics will be recorded. Baseline data to be recorded include:

- Demographics (age, sex)
- Vital signs (pre- and post-tube insertion)
- Mechanism of injury (blunt vs penetrating)
- Radiographic findings (pneumothorax, hemothorax or hemopneumothorax)
- Initial laboratory values (hematologic panel, chemistry panel, coagulation panel, toxicology, blood gases)
- Calculated injury severity score

The day of tube insertion will mark study day 0. Subjects will be monitored daily by study staff in the form of chart review for the duration of their hospitalization. A daily data log will be kept for each patient/ The information to be recorded includes:

- Volume of hemo/hemopneumothorax drainage
- Tube misplacement
- Tube migration
- Presence of air leak
- Need for additional thoracostomy tubes

- Need for operative intervention (VATS, thoracotomy)
- Date and time of pneumo/hemo/hemopneumothorax resolution as confirmed by a radiologist
- Date and time of chest tube removal
- Recurrent pnemo/hemo/hemopneumothorax
- Development of infection

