8.2 SAFETY AND OTHER ASSESSMENTS

The PI and the study team will meet biweekly to review the study procedures, enrollment (screening and randomization), implementation, protocol deviations, data collection, and adverse events. The biostatistics team will generate monthly reports for the study team which will monitor screening, enrollment, completeness of data for intervention implementation and outcomes, adverse events, and protocol deviations.

A medical monitor will determine the course of action necessary to meet safety goals and objectives. After the first 20 patients are enrolled and randomized, the study statisticians will generate a safety report for medical monitor review. An interim analysis for inferiority at 50% and 75% information accrual (see section 9.4.4: Planned Interim Analysis) will also be conducted. The medical monitor will recommend stopping if there is an increased incidence of procedure related serious complications or deaths in either treatment group that is found to be clinically significant.

Safety endpoints assessed by the study team and medical monitor will include:

- General safety assessments
 - Incidence of unanticipated serious adverse events related to chest tube size
- Thoracostomy tube related safety events
 - Hemodynamic instability post-insertion
 - Need for additional interventions (VATS, thoracotomy, chest tube replacement)
 - Procedure related deaths
 - Empyema
 - Re-accumulation/Recurrent pneumo- or hemothorax
 - Readmission to hospital within 90 days of insertion

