8.3.5 EXPECTEDNESS

The principle investigator is responsible for assessing the expectedness of an event. Expected safety events of interest for this study include: misplacement of tube, tube migration, death during insertion procedure, air leak, empyema, need for additional interventions (VATS, thoracotomy, chest tube replacement), catheter related blood stream infection and thoracostomy tube related hospital readmission. For the purposes of this study, deaths will be captured as clinical outcomes and do not need to be reported as SAEs unless determined by the principle investigator to be related to chest tube size.

All unanticipated problems that meet study definition will be reported to the IRB. An unanticipated problem is defined as “any serious adverse effect on health or safety or any life-threatening problem or death caused by, or associated with, a device, if that effect, problem, or death was not previously identified in nature, severity, or degree of incidence

in the investigational plan or application (including a supplementary plan or application), or any other unanticipated serious problem associated with a device that relates to the rights, safety, or welfare of subjects" (21CFR 812.3(s)).

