9.4.2 ANALYSIS OF THE PRIMARY EFFICACY ENDPOINT(S)

The rates of failure of drainage (primary outcome) will be estimated as proportions and compared between the two groups using a Chi-square test corrected for the non-inferiority hypothesis. We will present the findings using the difference in the proportions (rate in small group –rate in large group) and corresponding 95% upper confidence limit.

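### Read literally, the Aim I primary endpoint does not count a retained hemothorax evacuated by thoracotomy alone as a drainage failure

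*Combined protocol and SAP*

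**What the plan says.** Section 3 defines the Aim I primary endpoint as "Retained hemothorax requiring an additional intervention, either video-assisted thoracoscopic surgery (VATS) or additional thoracostomy tube placement". The synopsis (Section 1.1) and Section 9.1 use the same words. Thoracotomy is not among the two interventions named.

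Four other places name thoracotomy beside VATS:

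- Section 8.2, thoracostomy tube safety events: "Need for additional interventions (VATS, thoracotomy, chest tube replacement".
- Section 8.3.5, expected safety events: "need for additional interventions (VATS, thoracotomy, chest tube replacement".
- Section 6.2, daily log: "Need for operative intervention (VATS, thoracotomy".
- Section 1.3, footnote f, which defines the operative interventions to be collected as VATS, thoracotomy or tube replacement.

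Section 4.1 mentions operative intervention with VATS as its only example. It defines retained hemothorax by imaging alone, as "any residual blood that cannot be drained after 72 hours of thoracostomy as confirmed by imaging". Section 9.4.2 gives the outcome another name, without a new definition: "The rates of failure of drainage (primary outcome) will be estimated as proportions". No section says how a patient treated by thoracotomy alone is classified.

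**The concern.** Consider a patient who still has blood in the chest on imaging after 72 hours. The blood is removed at open operation, and neither VATS nor an additional tube is used for it. The first tube did not drain the chest, but the endpoint as worded records no event.

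In a non-inferiority trial, failures missed in the experimental arm favour the claim. Section 2.3.3 accepts that the 14 Fr tube may leave more retained blood, so an excess of missed failures in that arm is at least conceivable. The choice between VATS and thoracotomy is made by clinicians who can see the tube; the synopsis masks only the staff who collect and record data. Under the current list, part of the score therefore depends on the surgical approach as well as on whether drainage failed.

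**Working it through.** **Inputs.** Control failure rate: "We hypothesize the rate of drainage failure to be approximately 7% in the large 28 tube size group" (Section 9.2). Margin: "The margin of non-inferiority is defined as of 8" percentage points (Section 8.1). There are 126 patients per arm, with 80% power and α = 0.05 (Section 9.2). The result is judged by a 95% upper limit on the 14 Fr minus 28 Fr difference (Section 9.4.2). The documents give no thoracotomy rate, so the values of 1, 2 and 3 percentage points below are assumptions. One point is about 1.3 patients of 126.

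**Step 1: reproduce the plan's figure.** With both true rates at 7% and a one-sided α of 0.05:

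n = 2 × 0.07 × 0.93 × (1.645 + 0.842)² / 0.08² = 0.1302 × 6.183 / 0.0064 = 125.8, so 126 per arm.

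Power at 126 is 80.1%. A one-sided 0.025 would need 160 per arm. The stated size reproduces, so the point concerns the endpoint definition and not the arithmetic.

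**Step 2: chance of a false non-inferiority claim.** Let the true failure rates, thoracotomy included, lie exactly on the margin: 15% for 14 Fr and 7% for 28 Fr. Remove the uncounted thoracotomy-only cases to obtain the counted rates p₁₄ and p₂₈. Then

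P(claim) = Φ( [0.08 − (p₁₄ − p₂₈)] / SE − 1.645 ), with SE = √{[p₁₄(1 − p₁₄) + p₂₈(1 − p₂₈)] / 126}.

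| Points uncounted, 14 Fr / 28 Fr | Counted rates | SE | P(claim) |
|---|---|---|---|
| 0 / 0 | 15% v 7% | 0.0391 | 5.0% |
| 1 / 1 | 14% v 6% | 0.0375 | 5.0% |
| 2 / 2 | 13% v 5% | 0.0357 | 5.0% |
| 1 / 0 | 14% v 7% | 0.0384 | 8.3% |
| 2 / 0 | 13% v 7% | 0.0376 | 13.3% |
| 3 / 0 | 12% v 7% | 0.0368 | 20.3% |
| 2 / 1 | 13% v 6% | 0.0367 | 8.5% |

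For example, in the 2 / 0 row: (0.08 − 0.06) / 0.0376 − 1.645 = −1.113, and Φ(−1.113) = 13.3%. Exact binomial calculation with the Farrington-Manning test gives 8.2%, 13.0% and 19.7% for 1, 2 and 3 points lost from the 14 Fr arm only. Losses from the 28 Fr arm only work the other way: at 15% v 6%, (0.08 − 0.09) / 0.0382 − 1.645 = −1.907, or 2.8%.

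**Step 3: effect of the fix on power.** If the 7% already includes thoracotomy, 126 per arm stands. If it covers only VATS or an additional tube, and thoracotomy adds the same amount in both arms:

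| Rate in each arm | SE at 126 | Power at 126 | n per arm for 80% |
|---|---|---|---|
| 8% | 0.0342 | 75.7% | 143 |
| 9% | 0.0361 | 71.7% | 159 |
| 10% | 0.0378 | 68.1% | 174 |

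Power is Φ(0.08 / SE − 1.645).

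**The case against.** The strongest reply is that this is a gap in wording and not a contradiction. Lists for data capture and safety may properly be wider than an efficacy endpoint. Of the four places that name thoracotomy, only Sections 8.2 and 8.3.5 call it an additional intervention, and both are safety lists. Sections 1.3 and 6.2 list operations to be recorded, with no indication attached. Section 4.1 does not name thoracotomy at all, so a reader should not infer that the plan includes it in every list except the endpoint. All of this stands. It does not settle how the thoracotomy-only patient is scored.

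A reader might also infer that the plan declares such a patient a success. It does not; that result follows only from applying the closed list literally. Under the imaging definition in Section 4.1, or the label of drainage failure in Section 9.4.2, the same patient could be called a failure. The classification is therefore open, with no adjudication rule to close it.

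A third tempting inference is that a single uncounted case would overturn the trial. With 9 failures on 28 Fr, 11 on 14 Fr gives a Wald upper limit of 7.19 points and passes, while 12 gives 8.10 and fails. That is correct, but it is a chosen boundary case, and every trial has one. With 7% true failure in both arms, an exact binomial calculation puts a passing Wald result one 14 Fr event from failing in about 9% of trials.

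Finally, the cases would not be hidden. Thoracotomy is logged daily and is reviewed as a safety endpoint, so re-scoring is possible. This lowers the cost of the fix. It does not alter what the primary analysis counts, and re-scoring after outcomes are seen would look data-driven.

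**Conclusion.** The gap is real and should be fixed. As worded, the endpoint omits retained hemothorax evacuated by thoracotomy alone; a patient who also had VATS or an additional tube for the retained blood still counts.

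The size cannot be determined from the documents and may be negligible. Equal omission in both arms leaves the false-claim probability near 5%. It reaches about 8%, 13% or 20% only if 1, 2 or 3 points are lost from the 14 Fr arm alone, with true rates exactly on the margin. No figure in the documents supports or excludes such an imbalance. The documents therefore do not support the stronger conclusion that the trial counts its worst failures in favour of the 14 Fr tube.

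**What to change.** Before any outcome comparison, including the 50% interim analysis in Section 9.4.4:

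1. In Sections 1.1, 3 and 9.1, make the qualifying interventions VATS, thoracotomy for evacuation of retained blood, or placement of an additional thoracostomy tube.
2. Record the indication for each thoracotomy, so that one done for another reason is not counted.
3. Reconcile additional tube in the endpoint with tube replacement in Sections 1.3, 8.2 and 8.3.5. Section 7.1 says that replacement for inadequate drainage is collected as an outcome, without saying which one.
4. State in Section 9.2 whether the 7% control rate uses the amended definition. If it does not, restate power at 126 per arm: about 76%, 72% or 68% if thoracotomy adds 1, 2 or 3 points in both arms (assumed).

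The cost is a short amendment and one extra data item, the indication. Thoracotomy itself is already collected. The indication does introduce a judgement, and the decision to intervene remains with clinicians who know the tube size, so the change removes only the dependence on surgical approach. If item 4 shows that the 7% excludes thoracotomy, the sponsor must either accept the lower power or revisit the sample size (143, 159 or 174 per arm under the same assumptions).
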